4. SUBJECT POPULATIONS

4.1. Population Definitions

The **intent-to-treat (ITT) population** will comprise all randomized patients in the groups to which they were randomly assigned, regardless of their adherence with the entry criteria, regardless of the treatment they actually received, and regardless of subsequent withdrawal from treatment or deviation from protocol.

The **per-protocol (PP) population** will comprise all patients from the ITT population without any major protocol deviation that have received trial product and have completed at least one course of treatment.

All data analysed on the ITT or PP populations will be summarized using randomized treatment.

The **safety population** will comprise all patients that have received at least one administration of trial products.

All data analysed on the safety population will be summarized using actual treatment received.

The responsibility for defining the study populations and excluding patients from the analysis will be a joint decision by the sponsor, trial statistician, investigator and trial monitor. The patients to be excluded and the reasons for their exclusion must be documented and signed by those responsible prior to database release. The documentation must be stored together with the remaining trial documentation.

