Date of Initiation	Q1 2013						
Planned Date of	Q1 2018 (last patient last visit)						
completion	Recruitment duration = 36 months + 24 months follow-up						

2. Trial diagram

Figure 1: Study diagram

Patients included in the study will undergo successive courses of study treatment, for a duration up to 24 months. A course is defined as 28 days, with Day 1 being the first day the patient receive low-dose cytarabine (Figure 1: Study diagram).

Patient will have to attend a visit once a month, at the start of each course.

When study treatment is stopped (see required conditions in section 8.9), the visits will take place every 3 months until the 24 months study duration has been reached.

Refer also to section 8 for study treatment and assessments.

3. Introduction and rationale

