8.10 Study visits assessments and procedures

• Inclusion Visit (within max 4 weeks before treatment initiation):

During the inclusion visit, the following procedures/assessments will be performed:

- Patient information about potential study participation and obtaining the signed informed consent before any study related procedures;
- Patient demographics: date of birth, gender;
- ECOG performance status
- AML characteristics and assessment (see section 8.6): qualitative and quantitative parameters, primary diagnostic date, baseline values for bone marrow blast count, cytogenetic analysis, FAB and WHO classifications, including extramedullary AML assessment
- Medical history (relevant for the study condition) and concomitant medications
- General physical examination by systems and organs, including routine ECG, weight and height measurements
- Biological assessment (see section 8.7.1 for detailed items): date of sample taken; assessed and signed anonymized lab reports must be sent to sponsor/representatives Inclusion and exclusion criteria validation
- Patient registration in IWRS system
- Patient randomization if all criteria are met.
- Subsequent visits : from visit 1 onwards:
 - Disease evaluation (AML) (see section 8.6)
 - Clinical assessment: vital signs (height, weight, pulse, blood pressure systolic and diastolic), performance status (ECOG score), physical examination findings
 - Study treatment administration (low-dose cytarabine +/- GRASPA): details on date and time of administration are required
 - Patient quality of life: survey EORTC QLQ-C30, transfusion needs, hospitalizations from any cause (except scheduled protocol visit)
 - Biological assessment at D1, D5, D9, D13, D18, D23, D27 (see section 8.7.1 and table 4 for detailed items) instructions to be provided to patient in case of lab testing outside the site hospital; assessed and signed anonymized lab reports must be sent to sponsor/representatives as soon as possible after sampling
 - PK-PD and immunogenicity testing (see section 8.7.2, Table 4 and 5 and Appendix 3 for detailed instructions) only patients on arm B (under GRASPA treatment)
 - IAST (Irregular Antibodies Screening Test) at D9 only patients on arm B (under GRASPA treatment)
 - Review and assessment of any adverse event (refer to section 11 for details)
 - Record of any change in concomitant medications
 - Distribution of patient diary and instructions provided to patients for completion for each visit

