3. STUDY DESIGN

3.1. Synopsis of Study Design

This is a multicentre, open label, randomized 1:2 (control versus GRASPA), controlled phase IIb trial in Europe, evaluating efficacy and tolerability of GRASPA. The trial follows the scheme below:

In both treatment and control arms, patients will be treated with subcutaneous LDAC as 40 mg daily (either one single dose of 40 mg or 20 mg twice daily according to local practice) for 10 consecutive days per course, each course occurring every 28 days \pm 3 days, for a duration up to 24 months. Each period of 28 days constitutes a cycle of chemotherapy. The dosage could be adjusted to 20 mg once daily in case of toxicities; a higher dose is also acceptable if required by the patient's status, at the investigator's decision.

In the experimental group, the patients will receive subcutaneous LDAC, as described above, and GRASPA (100 U/kg) given as an intravenous infusion at Day 11 of each 28 day course.

Patients will be required to attend a visit once a month, as the course begins.

When study treatment is stopped (main expected reasons are limiting toxicity, PD, or no evidence of treatment benefit), the visits will take place every 3 months until 24-months study duration has been reached.

An Independent Data Monitoring Committee (IDMC) was set-up for regular data reviews for safety: they reviewed the tolerance of GRASPA when 30 patients had been enrolled, to evaluate limiting toxicities defined as one of the following:

- grade 3 or 4 pancreatic toxicity
- grade 3 or 4 hepatic toxicity, allergic reaction, or coagulation event

- other non-hematologic grade 4 toxicity or requiring treatment change at investigator's decision

Specific attention is paid on type II diabetic patients treated with oral hypoglycemic agents for their diabetes, randomized to LDC + GRASPA.

The IDMC also reviewed safety and tolerance of GRASPA when 60 patients had been enrolled, at the end of recruitment and when 60 PFS events had been observed.

Additional information is provided in the IDMC Charter and the minutes of the IDMC meetings.

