5.6. Efficacy Evaluation

All efficacy analyses will be performed on the ITT population. Analyses on the primary efficacy endpoint will be repeated on the PP population.

Primary Endpoint Definition and Analysis

The primary endpoint, OS, will be defined as the time elapsed between date of randomization and date of death (or censoring) from any cause. Any patient not known to have died at the time of analysis will be censored based on the last recorded date on which the patient was known to be alive.

The primary objective of the trial is to estimate whether GRASPA plus LDAC is more promising than LDAC alone with respect to OS in subjects from 65 to 85 years old with newly diagnosed AML unfit for intensive chemotherapy.

Overall survival will be summarized by treatment group for the ITT population. Summaries will include the number of patients who died during the study, the number of patients who didn't die during the study (censored) with the date of censoring equal to the date that the patient was last known to be alive. Median time-to-event will be estimated from a Kaplan-Meier analysis, with associated survival curves produced. The p-value for this analysis will be provided from the stratified log-rank test, with stratification variable of type of ECOG performance status (0 or 1 versus 2) and will compare the overall survival curves between the two treatment groups. In addition, the hazard ratio and its associated 95% CI will be estimated from a stratified Cox proportional hazards model using the same strata as the Kaplan-Meier analysis (ECOG status) and censoring rules. Forest plots for the OS hazard ratios for the subgroups detailed in Section 4.2.6 will also be produced.

OS event rates at Months 12 and 24 will be summarized by treatment group for the ITT population. Summaries will include the event rate for each treatment group from the Kaplan-Meier analysis, using the estimated proportions at Month 12 and 24. A 95% CI for the difference in event rates between the treatment groups will also be provided.

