5.6.1. Sensitivity Analyses for the Primary Endpoint

The analyses described in Section 4.6 will also be repeated on the PP population and separately for patients recruited before and after the protocol amendment to assess sensitivity of results to protocol compliance and amendment.

A further sensitivity analysis will be undertaken based on a stratified Cox Model, stratified for PS (0 or 1 versus 2), and including age (< 70 / ≥ 70) and Karyotype (Intermediate risk / High risk) as covariates.

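### Requiring a completed 28-day course for the per-protocol set removes course-1 deaths, so the PP overall-survival hazard ratio cannot register excess GRASPA deaths in that course

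*SAP*

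**What the plan says.** SAP 4.1 builds the PP set from ITT patients free of major deviations "that have received trial product and have completed at least one course of treatment". Protocol 15.1 has the same rule. Neither document says when a course counts as completed, makes an exception for early death, or sets a landmark.

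The timing comes from elsewhere:

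- **Course length.** Protocol section 2: "A course is defined as 28 days, with Day 1 being the first day the patient receive low-dose cytarabine".
- **GRASPA.** SAP 3.1: "given as an intravenous infusion at Day 11 of each 28 day course". Cytarabine runs from Day 1 to Day 10 in both arms.
- **OS clock.** SAP 5.6: "OS, will be defined as the time elapsed between date of randomization and date of death (or censoring) from any cause".
- **Start of treatment.** Protocol 8.10 places randomisation at the inclusion visit, which may be up to four weeks before treatment starts.

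SAP 5.6.1 says the OS analyses "will also be repeated on the PP population" and separately for patients recruited before and after the amendment, "to assess sensitivity of results to protocol compliance and amendment". It also names a third sensitivity analysis, a stratified Cox model adjusted for age and karyotype. SAP 5.6.2 assesses the secondary endpoints on both ITT and PP.

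**The concern.** On the 28-day definition, completing a course means being alive and on treatment to the end of course 1. That is a post-randomisation outcome, not a measure of adherence: a patient who takes every scheduled dose and dies on Day 20 has deviated from nothing, yet leaves the PP set. Both arms face the same rule, but only arm B receives a second agent inside the excluded window, on Day 11.

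The PP result carries some weight here. SAP section 1 says conclusions will not rest on the primary analysis alone but on the effect across a range of endpoints, and SAP 5.1 judges promise by whether the OS HR is 0.80 or lower. If GRASPA caused early deaths, the ITT HR would rise and the PP HR would not. The PP run would then look more favourable for a reason unrelated to compliance. Early death is a recognised risk in this population: SAP 3.2 gives it as the reason for stratifying by performance status.

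**Working it through.** The plan states no figure for the PP set. Its OS benchmark reproduces: SAP section 1 gives medians of 6.4 and 8.0 months, and 6.4/8.0 = 0.80.

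**1. Deaths before Day 28 at the plan's own medians.** Take exponential survival with Day 1 set at randomisation. Then P(death by t) = 1 − 2^(−t/median), with t = 28/30.4375 = 0.92 month.

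| Medians (control / GRASPA) | Control, n = 41 | GRASPA, n = 82 |
|---|---|---|
| 6.4 / 8.0 months (SAP section 1) | 1 − 2^(−0.92/6.4) = 9.5%, 3.9 patients | 1 − 2^(−0.92/8.0) = 7.7%, 6.3 patients |
| 2 / 3.5 months (Protocol 15.3.1; SAP 5.1 calls these PFS medians) | 27.3%, 11.2 patients | 16.7%, 13.7 patients |

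Any gap between randomisation and Day 1 adds further deaths before the end of course 1.

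**2. No early harm.** Piecewise-exponential simulation, control median 6.4 months, 12-month censoring, unstratified Cox model.

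- Equal hazards throughout: ITT 1.00, PP 1.00.
- GRASPA hazard multiplied by 0.8 from Day 10 onward: ITT 0.81, PP 0.80. Medians rise from 6.4 to 7.3 and from 7.9 to 8.9 months. Under exponential survival the rise is the 0.92 month of guaranteed survival.

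**3. Excess arm B deaths on Days 11 to 28 and no effect otherwise.** The excess rates are assumptions, shown as a range. The arm B fraction excluded is 1 − 0.905 × (1 − excess), against 9.5% (3.9 of 41) in control.

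| Assumed excess | Arm B excluded | ITT HR | PP HR, 28-day reading | PP HR, end-of-dosing reading |
|---|---|---|---|---|
| 5% | 14.0%, 11.5 of 82 | about 1.06 | about 1.00 | about 1.07 |
| 10% | 18.5%, 15.2 of 82 | about 1.13 | about 1.00 | about 1.14 |
| 15% | 23.1%, 18.9 of 82 | about 1.22 | about 1.00 | about 1.23 |

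The HRs are large-sample values with 12-month censoring. The last column treats a course as completed at Day 10 in arm A and Day 11 in arm B. With full follow-up instead of 12-month censoring, the ITT values are 1.05, 1.10 and 1.16, and the 28-day PP value is still 1.00.

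**4. Early harm followed by later benefit.** Suppose the arm B hazard is tripled on Days 10 to 28 (assumed) and the HR is 0.80 afterwards. ITT is 0.99 and PP is 0.80. In simulated trials of 41 and 82 patients, the chance of an HR at or below 0.80 is 18% in ITT and 50% in PP.

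**5. Why the PP value does not move.** The PP set contains no deaths before Day 28, so its Cox estimate uses only risk sets after that day. Starting the clock at Day 28 subtracts the same constant from every time, leaves the order of events unchanged, and so gives the identical HR.

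**The case against.** The strongest reply is that nothing is hidden. ITT is the primary set and keeps every death. SAP 8.1 lists tables of deaths, of deaths within 28 days of the last study drug, and of reasons for PP exclusion. SAP 4.1 requires exclusions to be documented and signed before database release. A gap between the ITT and PP estimates would itself be a warning. All of this stands, and it limits the point to a supportive analysis. A reader might infer that the plan conceals early GRASPA deaths; the documents do not support that.

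A reader might also infer that the rule favours GRASPA in general. It does not. With equal early mortality the HR is unchanged, and at the SAP's own medians the rule drops a larger share of controls than of GRASPA patients. Bias in the HR needs early loss that differs by arm, and the documents give no figure for such an excess.

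A third inference is that timing OS from randomisation causes the problem, so that a Day 28 landmark would cure it. Step 5 shows otherwise: the landmark corrects the medians and leaves the HR as it was.

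Finally, *completed* is undefined. If it meant the last scheduled dose of the course, deaths after the Day 11 infusion would stay in and the harm would remain visible. The stated 28-day course points the other way, and leaving the choice to data review in an open-label trial is itself a reason to settle the wording.

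**Conclusion.** The point holds for the PP analysis on the documents' 28-day definition of a course. The completed-course condition selects on the outcome, and the PP OS HR does not respond to excess GRASPA deaths in course 1: about 1.00, against an ITT HR of about 1.06, 1.13 or 1.22 at an assumed 5, 10 or 15% excess. Harm after course 1 stays visible. Without differential early loss, the consequence is only that PP medians are about 0.9 month too long.

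The sizes rest on exponential survival with a control median of 6.4 months, Day 1 at randomisation, and assumed excess death rates. Toxicity stops were not modelled. The scope is one of the three OS sensitivity analyses in SAP 5.6.1 and the PP runs of the secondary endpoints; the primary analysis is unaffected. The wording should be changed because, as written, the PP run does not do what SAP 5.6.1 says it is for.

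**What to change.** Either of two changes to SAP 4.1 removes the selection on death:

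- define PP as no major protocol deviation plus at least one dose of cytarabine in both arms, without the completed-course condition; or
- keep the condition, but state that death or a protocol-permitted toxicity stop during course 1 is not grounds for exclusion.

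With either change, report the numbers excluded from PP by arm and reason. Because Protocol 15.1 carries the same definition, record the departure in SAP section 6. Do not offer a Day 28 landmark as the remedy.

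The cost is wording plus an arm-by-reason layout for the exclusion table already listed in SAP 8.1; no new data are needed. The SAP is due for signature before database lock, so the change belongs before then. One small drawback is that some arm B patients who died before the Day 11 infusion would be in the PP set without having received GRASPA.

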8.11 End of study treatment

Patients will stop study treatment in following situations:

- Disease relapse or presence of a resistant disease, unless the investigator considers that the patient has a clinical benefit from continuing the treatment. In this case, the investigator should continue to perform the same study visits as long as considered clinical beneficial.
- Occurrence of GRASPA-related toxicity, such as:
 - Grade 3 or 4 pancreatic toxicity
 - o Grade 3 or 4 hepatic toxicity, allergic reaction, or coagulation event
 - o other non-hematologic Grade 4 toxicity

Patient assessment should continue as planned until evidence of relapse or presence of a resistant disease, in which case, patient will be followed up for survival.

- Patient unwilling to continue
- No evidence of study treatment benefit at investigator's decision

9. Investigational product: GRASPA

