3.5.3. Safety Variables

All subjects who received at least one dose of investigational products will be included in the safety analyses. Safety data will be summarized using actual treatment received, regardless of randomized treatment.

Safety and tolerability will be assessed in terms of AEs, SAEs, laboratory data and vital signs which will be collected for all subjects. AEs will be coded according to the Medical dictionary for regulatory activities (MedDRA) version 15.1 or higher. The intensity of AEs will be graded according to the NCI-CTCAE (version 4.0).

AEs, AE leading to study treatment discontinuation, AE related to study treatment, and SAEs will be listed individually by subject, and summarized by System Organ Class (SOC) and Preferred Term (PT) by treatment group. Summary of AEs with NCI-CTCAE grade 3 or 4 and most frequent PT will also be provided.

Specific attention will be given to NCI-CTCAE Grade 3 or 4 of pancreatic toxicity, Grade 3 or 4 of hepatotoxicity, allergic reactions or coagulation disorders, known to be potentially related to L-asparaginase as well as to hypoproteinemia and hyperglycemia/diabetes events.

Specific safety endpoints will include the following:

- 1) Safety of GRASPA in combination with low-dose cytarabine, with specific attention to :
 - a. Grade 3 or 4 of pancreatic toxicity
 - b. Grade 3 or 4 of hepatic toxicity, allergic reaction or coagulation event
 - c. Grade 3 or 4 of hypoproteinemia or hyperglycemia/diabetes
 - d. All other non-hematologic Grade 4 toxicities

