5.2.9. Visit Windows

Assessments are taken at specific study days in relation to the first day of LDAC (Study Day 1). LDAC is administered each day following and including Day 1, for 10 consecutive days (D1-D10). Patients in the treatment group are also administered GRASPA at Day 11. This will occur each course, which is 28 days +/- 3 days.

Biological assessments will be performed (if applicable) at D1, D5, D9, D13, D18, D23 and D27 during each course (+/- 2 days). The quality of life questionnaire and information about both hospitalizations and transfusion needs will be completed at each visit.

Follow-up visits will occur at the end of study treatment every 3 months +/- 2 weeks (i.e. M3, M6, M12,...). At minimum, a phone call will be performed every 4 months +/- 1 week after end of treatment for safety assessments.

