5.8.1. Adverse Events

Safety and tolerability will be assessed in terms of AEs, SAEs, laboratory data and vital signs, which will be collected for all subjects. The AE term (Investigator term) will be assigned to the lowest level term (LLT), and a preferred term (PT) will be classified by a high level term (HLT), a high level group term (HLGT) and a system organ class (SOC) according to the Medical Dictionary for Regulatory Activities (MedDRA) thesaurus, Version 15.1 or higher depending on the latest version available during the study. The intensity of AEs will be graded according to the NCI-CTCAE (version 4.0).

An overview of the number of patients with AEs and the corresponding number of AEs will be presented through tables and listings:

- Total AE count
- Any AE
- Any treatment-related AE (Cytarabine and/or GRASPA®)
- Any AE of CTCAE grade ≥ 3
- Any AE of CTCAE grade = 4
- Any treatment-related (Cytarabine and/or GRASPA®) AE of CTCAE grade ≥ 3
- Any severe treatment-related (Cytarabine and/or GRASPA®) AE
- Any AE with outcome of death
- Any serious AE

- Any treatment-related (Cytarabine and/or GRASPA®) serious AE
- Any AE leading to permanent discontinuation
- Any treatment-related (Cytarabine and/or GRASPA®) AE leading to permanent discontinuation (Action taken=Withdrawn)
- Any AE leading to temporary discontinuation
- Any treatment-related (Cytarabine and/or GRASPA®) AE leading to temporary discontinuation (Action taken=Reduced)

An AE will be considered as “treatment-related” if the relationship to study treatment is ticked “possible,” “probable” or “certain/definite”.

For subject counts, subjects are included only once, even if they experienced multiple events in that category.

All the following summaries will be displayed by treatment groups on the safety population:

- All AE by System Organ Class (SOC) term, Preferred Term (PT)
- AE Experienced by $\geq 5\%$ of Subjects by SOC term and PT
- Treatment-related (Cytarabine and/or GRASPA®) AE by SOC term and PT
- AE of CTCAE grade ≥ 3 by SOC term and PT
- AE of CTCAE grade = 4 by SOC term and PT
- Treatment-related (Cytarabine and/or GRASPA®) AE of CTCAE grade ≥ 3 by SOC term and PT
- Severe treatment-related (Cytarabine and/or GRASPA®) AE by SOC term and PT
- AE with outcome of death
- Serious AE
- Treatment-related (Cytarabine and/or GRASPA®) serious AE
- AE leading to permanent discontinuation
- AE leading to temporary discontinuation

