14.3.1.2.6	Incidence of Treatment Related Treatment Emergent Serious Adverse Events by Preferred Term	Safety
14.3.1.2.7	Incidence of Treatment Emergent Adverse Events of Special Interest by Preferred Term	Safety
14.3.1.2.8	Incidence of Treatment Emergent Adverse Events of Special Interest with Toxicity Grade of 3 or 4 by Preferred Term	Safety
14.3.1.2.9	Incidence of Treatment Emergent Adverse Events Occurring in at least 5% of Patients in either Treatment Group by MedDRA Preferred Term	Safety
14.3.1.3	Listing of Treatment Emergent Adverse Events Leading to Either GRASPA or Chemotherapy Withdrawal	Safety

Table/Figure Number	Output Title	Analysis Set
	Deaths	
14.3.2.1	Deaths and Deaths within 28 Days After Last IMP Administration	Safety
14.3.2.2	Listing of All Deaths	Safety
	Clinical Laboratory Data	
	Biochemistry	
14.3.3.1.1	Biochemistry – Summary of Shift From Baseline to Worst Post-Baseline Results	
14.3.3.1.2	Biochemistry – Summary Statistics for Clinically Significant Parameters by Treatment Group and Time	
	Hematology	
14.3.3.2.1	Hematology – Summary of Shift From Baseline to Worst Post-Baseline Results	Safety
14.3.3.2.2	Hematology – Summary Statistics for Clinically Significant Parameters by Treatment Group and Time	Safety
	Coagulation	
14.3.3.3.1	Coagulation – Summary of Shift From Baseline to Worst Post-Baseline Results	Safety

Table/Figure Number	Output Title	Analysis Set
14.3.3.3.2	Coagulation – Summary Statistics for Clinically Significant Parameters by Treatment Group and Time	Safety
	Other Safety Parameters	
	Vital Signs Data	
14.3.4.1.1	Vital Signs – Descriptive Statistics for Change From Baseline	Safety
14.3.4.1.2	Vital Signs – Listing of Clinically Significant Values	Safety
14.3.4.2	ECOG Performance Status – Shift From Baseline to Worst Post-Baseline Value	Safety

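### Grouping safety data by treatment actually received, when GRASPA starts only on Day 11, moves arm B's pre-infusion deaths into the control column

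*SAP*

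**What the plan says.** SAP 4.1 admits to the safety population patients who "comprise all patients that have received at least one administration of trial products" and sets the grouping rule: "All data analysed on the safety population will be summarized using actual treatment received". SAP 3.5.3 has the same entry condition in other words ("All subjects who received at least one dose of investigational products will be included in the safety analyses") and a firmer grouping rule: "Safety data will be summarized using actual treatment received, regardless of randomized treatment". Protocol 15.3.3 repeats that rule, and the Protocol synopsis and 6.2 also group safety data by treatment received. ITT and PP data, by contrast, are grouped by randomised treatment (SAP 4.1).

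On timing, SAP 5.2.9 gives cytarabine on Days 1–10 in both arms and adds: "Patients in the treatment group are also administered GRASPA at Day 11". Protocol 9.2 agrees. Protocol 8.4 allows a delay of up to one week after a supply failure and provides for patients switched to other treatment before their first GRASPA administration.

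On outputs, SAP 5.8.1 says of the AE tables: "All the following summaries will be displayed by treatment groups on the safety population". The table shell there has columns for GRASPA + LDAC, LDAC and Total only. Table 14.3.2.1 in SAP 8.1, "Deaths and Deaths within 28 Days After Last IMP Administration", is assigned to the Safety set.

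**The concern.** For the first ten days the two arms receive the same drug. To enter the GRASPA column under an actual-treatment rule, a patient must survive and stay on treatment until the infusion. Arm B patients who do not are added to a control column that starts at half the size. Patients are therefore sorted by early outcome, and the GRASPA column contains no pre-infusion deaths by construction. Nothing in either document keeps a patient given only cytarabine with arm B.

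At stake are the Safety-set death table and the summaries of fatal AEs and of AEs leading to permanent discontinuation, all of which would favour GRASPA. Other AE tables could move either way. Moved patients have at most about ten days of exposure (longer if the infusion is delayed), so they can lower the control rate of cumulative or late non-fatal events. Protocol 11.1.2.1 also keeps progression deaths out of SAE reporting. SAP 1 draws its conclusion on activity from the totality of evidence, so a death table with a built-in lean will be read beside overall survival.

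A related gap is that IMP in Table 14.3.2.1 is undefined. The heading of Protocol section 9 reads "Investigational product: GRASPA", while SAP 3.5.3 uses the plural. If IMP means GRASPA only, arm A has no last-IMP date and the 28-day row cannot compare arms.

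**Working it through.** The documents contain no figure on this point to reproduce: neither a pre-Day-11 death rate nor a count of arm B patients never infused. What follows is an illustration.

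**Inputs from the documents**
- Arm sizes 41 and 82 (SAP 5.1)
- Control median OS 6.4 months (SAP 1)
- First GRASPA on Day 11 (SAP 5.2.9)

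**Assumptions**
- Constant hazard, the same in both arms
- All patients dosed with cytarabine
- Only deaths move patients
- Range for the Day 10 death rate p: 1%, 2%, 3.5%, 5%
- True rate of death within 28 days of last dose: 25% or 40%, with cytarabine counted as IMP

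**Step 1, early deaths.** h = ln 2 / (6.4 × 30.44) = 0.00356 per day. P(death by Day 10) = 1 − exp(−10h) = 3.5%. The same hazard gives 9.5% by Day 28, 72.7% by 12 months and 92.6% by 24 months.

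**Step 2, patients moved.** m = 82p. At p = 3.5%, m = 2.87, and the columns become 43.87 (control) and 79.13 (GRASPA).

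**Step 3, apparent death rates.** With true rate q in both arms, control = (41q + m)/(41 + m) and GRASPA = (82q − m)/(82 − m).

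At p = 3.5% and 12 months:
- control = (41 × 0.727 + 2.87)/43.87 = 74.5%
- GRASPA = (82 × 0.727 − 2.87)/79.13 = 71.7%

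False gap, control minus GRASPA, in percentage points:

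| p | moved | 12 months (true 72.7%) | 24 months (true 92.6%) | 28 days after last dose, q = 25% | same, q = 40% |
|---|---|---|---|---|---|
| 1% | 0.8 | 0.8 | 0.2 | 2.2 | 1.8 |
| 2% | 1.6 | 1.6 | 0.4 | 4.4 | 3.5 |
| 3.5% | 2.9 | 2.8 | 0.8 | 7.6 | 6.1 |
| 5% | 4.1 | 3.9 | 1.1 | 10.8 | 8.6 |

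At p = 3.5% the 28-day row reads 29.9% against 22.3% for q = 25%, and 43.9% against 37.8% for q = 40%. Deaths by study Day 28, which is not a planned row, would read 15.4% against 6.2% when the truth is 9.5% in both.

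**Step 4, how often.** P(at least one moved) = 1 − (1 − p)^82, which is 56% at p = 1%, 81% at 2% and 95% at 3.5%. A single moved death at q = 25% gives 26.8% against 24.1%, a gap of 2.7 points. In 20,000 simulated trials with equal 6.4-month medians, control showed the higher 12-month death rate in 62% under the actual-treatment rule and in 47% when grouped by randomised arm.

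**Step 5, adverse events at p = 3.5%.** With overall rate r and rate s in moved patients, control = (41r + ms)/(41 + m) and GRASPA = (82r − ms)/(82 − m).
- r = 90%, s = 50%: 87.4% against 91.4%, which is against GRASPA.
- r = 15%, s = 100% (a fatal or discontinuation AE in every moved patient, the upper end): 20.6% against 11.9%, towards GRASPA.
- Asparaginase-class events occurring only after infusion: the GRASPA rate rises by 82/(82 − m) − 1, from 1.0% relative (p = 1%) to 5.3% (p = 5%).

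**Step 6, patients who stop alive.** If 5% or 10% of arm B also stopped alive before infusion, the 12-month gap at the 6.4-month median would fall from 2.8 to 2.5 or 2.3 points. The direction does not change.

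**The case against.** The documents often use treatment to mean the assigned regimen: Protocol 7.4 and SAP 3.2 allocate patients to treatment A or B, and B is cytarabine plus GRASPA. On that reading an arm B patient who starts cytarabine has started treatment B and stays there. Population assignment is also a joint, documented decision before database release. However, the text says actual treatment overrides the randomised arm, and neither the joint decision nor the data review defines actual treatment. The regimen reading is what the SAP should say, but it does not say it.

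Some randomised-arm output already exists. SAP 5.6 counts deaths by group on the ITT set, Table 14.3.1.1.3 is a safety summary labelled ITT, and the disposition counts and death listing 14.3.2.2 would show the moved patients. These limit the harm and let a careful reader detect it, but they leave the Safety-set tables uncorrected.

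The largest gaps rest on unsourced inputs. The 25% and 40% rates are assumed, and the 28-day bias needs IMP to include cytarabine. That stands, so those figures show scale only. The switch in Protocol 8.4 follows a supply failure, not a bad outcome. It shows that never-infused arm B patients are foreseen, and does not itself sort by prognosis.

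Finally, for asparaginase-class toxicity the infused patients are a natural denominator, and grouping by arm dilutes those rates slightly. That is true, and a Day 11 landmark table answers it.

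**Conclusion.** The rule is wrong as written and should be fixed. The direction for death tables follows from the rule and the schedule: any arm B death between the first cytarabine dose and the first infusion leaves the GRASPA column and enters control. The size is not known from the documents. Over Day 10 death rates of 1% to 5%, the false gap is 0.8 to 3.9 points for all deaths at 12 months and 0.2 to 1.1 points at 24 months. For deaths within 28 days of last dose it is 1.8 to 10.8 points, if IMP includes cytarabine and the true rate is 25% or 40%. These figures assume a constant and equal hazard and that all patients are dosed. If nobody dies or stops before infusion, there is no bias. AE tables shift in either direction, towards GRASPA for fatal and discontinuation events. ITT overall survival and its hazard ratio, on which the promise of the drug is judged, are not touched.

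**What to change.** Before database lock, amend SAP 3.5.3 and 4.1, with matching wording in the Protocol synopsis, 6.2 and 15.3.3:

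- Summarise safety by randomised arm for every patient who received at least one dose of cytarabine or GRASPA. Reassign only an arm A patient who actually received GRASPA.
- Report the number of arm B patients never given GRASPA.
- State whether IMP in Table 14.3.2.1 includes cytarabine.
- Optionally, add a Day 11 landmark table for both arms, limited to patients alive and on treatment at Day 11 with events counted from then, to give rates in GRASPA-exposed patients.

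The cost is SAP and Protocol wording and one grouping variable. The drawback is that the few never-infused arm B patients dilute GRASPA-specific rates, by about 3.5% relative under the 3.5% illustration.
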